### **Outcomes {12}**

The primary outcome of interest is the following:

1. Household COVID-19 testing

Household COVID-19 testing uptake at the 9-month follow-up (9MFU) will be the primary outcome of interest. Our project will document testing uptake that is either administered by nurses or self-administered during home visits in the experimental arm, as well as self-reported information regarding COVID-19 testing uptake by study participants in the treatment and control groups. Participants will be asked whether they have received COVID-19 testing in the past three months, as well as about variables collected via the COVID-19 Symptoms, Diagnoses, and Testing scale. The COVID-19 Symptoms, Diagnoses, and Testing scale is adapted from the COVID-19 Cannabis Health Questionnaire. Specifically, participants will be asked questions regarding whether they are currently sick with an illness that might be related to COVID-19, any symptoms the participant experienced in the past three months, and the result of the participant's last COVID-19 test.

The secondary outcomes of interest are:

1. Household COVID-19 Testing Uptake

All medical services delivered by nurses during home-visits (such as COVID-19 test administration) will be carefully documented by the investigative team. At the time of the 6-month-follow-up (6MFU) assessment, the project team will obtain self-reported information regarding COVID-19 testing uptake by study participants in the treatment and control groups. Respondents will be asked whether they have received COVID-19 testing in the past six months. Respondents will also be asked questions from the COVID-19 Symptoms, Diagnoses, and Testing scale regarding whether they are currently sick with an illness that might be related to COVID-19, any symptoms the participant experienced in the past six months, and the result of the participant's last COVID-19 test.

2. COVID-19 control measure uptake

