There are several mediating variables of interest including: knowledge and self-efficacy for COVID-19 prevention, testing salience, habitual processes, and medical mistrust. These measures are captured in the baseline, 6-month, and 9-month questionnaires. **Figure 2** features all mediating variables considered for these analyses.

Created Variables

We will create summary scores for all survey scales using validated scoring procedures. We will create difference variables (e.g., 6 month-baseline, 9 month – 6 month, 9 month-baseline) for time varying variables (e.g., vaccination status, COVID-19 exposure, employment status) measured at multiple time points.

Figure 1: Consort Flow Diagram

[figure not shown]
[figure not shown]

Figure 2: NCFP Theoretical Model

Design.

The randomized control trial will include 150 households, and 400 individual household members who will be randomized into 2 arms with parallel assignment in a 2:1 ratio, intervention:control. Participants in the intervention arm will receive the Nurse-Community Health Worker-Family Partnership intervention. The control arm will receive standard access to NYC Department of Health COVID-19 testing sites and standard COVID-19 public health messaging for NYCHA residents.

Framework.

With regard to hypothesis testing, the trial will utilize a superiority hypothesis testing framework. The study team will compare differences between baseline data and data collected at the 9-month follow-up timepoint to assess whether or not the intervention group had a higher efficacy in regards to the outcomes of interest than that of the control group.

Randomization.

After the baseline assessment and confirmation of eligibility, treatment allocation will be determined using a household-level randomization scheme of 2:1. The study team will randomize households using the password-protected REDCap desktop app using a predetermined randomization algorithm entered into the EDC system.

Interim Analyses.

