The data team will conduct interim analyses every 6 months during the duration of the trial. The analysis will review data on recruitment, participant characteristics, protocol compliance, and study outcome. This analysis will also assess the differential proportion of self-reported COVID-19 infection between the two treatment groups (a safety assessment of the trial primary outcome). There are no planned adjustments of the significance level due to interim analysis. In addition, cross-sectional analyses will be completed after data collection for each time point (baseline, 6-month, 9-months).

Final Analysis.

The final analysis will be conducted once outcome data for all enrolled participants is collected, outside of participants who withdrew early or were lost to follow-up. If the trial is not stopped early for any reason, the final analysis will be conducted using available data. Since the primary outcome is clearly defined, the level of

significance of this study will not be adjusted for multiplicity. All hypothesis tests will be 2 sided, with a 95% confidence interval.

Trial Population.

Inclusion Criteria

- Residence in one of the NYCHA complexes in Mott Haven, South Bronx
- English or Spanish-speaking
- Age 10 years or older
- Willing and able to provide informed consent or assent

Exclusion Criteria

- Non-resident of one of the NYCHA complexes in Mott Haven, South Bronx
- Does not speak English nor Spanish
- Younger than 10 years old, unless household index case tests antigen positive. In this instance, all members of family will be included.
- Unwilling or unable to provide informed consent or assent

Screening Data

Screening data will be summarized on a quarterly basis during the recruitment period, as well as in final reports, those invited to participate in the study will be classified as eligible or ineligible in order to describe the representativeness of the study population.

Withdrawal/Follow Up

The team expects a low level of attrition from withdrawal or loss to follow-up from the study due to the infrequency of study assessments, the community engaged research approaches used in the intervention, the average length of residency in NYCHA housing, and the duration of the follow up period. Withdrawal and lost to follow up data will be reported with the 6-month and 9-month follow up data. Demographic characteristics of participants who withdraw or are loss to follow-up will be examined and compared to those who complete the study.

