Consensus has yet to be determined on the precise power calculations for multilevel models[1-3]. Subramanian and other respected scholars in multilevel modeling argue that if the purpose of the multilevel model is to estimate the variation of level-1 variables, the size of the level-1 variable is really the driving factor [2,3]. Power for the proposed study was calculated using Power Analysis and Sample Size software (PASS 2020) based on household level randomization, individual level outcomes using conservative estimates and adjusting for 15% attrition and allowing for subgroup analyses [4]. A test for the difference in two proportions using a mixed model based on a clustered 3-Level Hierarchical Design with level-3 (household) 2:1 intervention: control randomization. The total sample size of 300, obtained from 100 level-3 units (households) in the intervention group and 50 level-3 units in the control group with an average of 2 level-2 units (individuals) per level-3 unit (household) and an average of 3 level-1 units (timepoints) per level-2 unit (individual), achieves >80% power to detect a difference between the group proportions of at least 0.15. The proportion in group 2 is 0.10. The correlation of level-1 units within a level-2 unit is <0.7. The correlation of level-2 units within a level-3 unit is <0.3. A test based on a mixed-effects logistic regression is anticipated at a significance level of 0.05.

References:

2. Snijders AT. Power and sample size in multilevel modeling. 2005;3:1570-1573.
3. NCSS LLC. PASS 2020 Power Analysis and Sample Size Software; 2020. ncss.com/software/pass.
6. Robinson TJ. Multilevel Analysis: Techniques and Applications. *J Am Stat Assoc*. 2003;98(462):496-496.
7. Hox JJ. Multilevel Analysis: Techniques and Applications. Psychology Press; 2002.
8. Joreskog, K. G., & Sorbom D. (1988). PRELIS: A Program for Multivariate Data Screening and Data Summarization. A Preprocessor for LISREL. Chicago: SSI, Inc.
9. Joreskog, K. G. (1978). Structural analysis of covariance and correlation matrices. *Psychometrika*, 43, 443-477.

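### The SAP's superiority statement compares baseline-to-9-month differences, which conflicts with the 9-month uptake endpoint and the mixed-effects logistic test, and no baseline-adjusted primary analysis is named

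*SAP*

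**What the plan says.** **Endpoint.** Protocol, Outcomes {12}: "Household COVID-19 testing uptake at the 9-month follow-up (9MFU) will be the primary outcome of interest". SAP, Definition of Primary Outcomes, gives the item as a yes/no answer about testing in the past three months.

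**How superiority is judged.** The SAP's Framework paragraph is the only place that says so directly: "The study team will compare differences between baseline data and data collected at the 9-month follow-up timepoint". Under Created Variables the SAP adds "We will create difference variables", including 9 months minus baseline, for time-varying variables. Its examples are vaccination status, exposure and employment.

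**Models.** SAP, Analysis for Aim 4, plans multilevel logistic models at each timepoint. SAP, Longitudinal Analysis, writes out a three-level random-intercepts logistic model and a test of two proportions from it. The response in that equation is the logit of the outcome at time t, not a difference. The covariates named as examples do not include baseline testing, and no arm or arm-by-time term is named.

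**Power.** SAP, Power and Sample Size (repeated in Protocol, Sample size {14}), describes a three-level design with three timepoints that "achieves >80% power to detect a difference between the group proportions of at least 0.15". It adds "The proportion in group 2 is 0.10" and "A test based on a mixed-effects logistic regression is anticipated at a significance level of 0.05".

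**The concern.** A statistician following this SAP could run three different primary tests: a comparison of changes from baseline, a 9-month comparison, or a longitudinal model over three timepoints. They do not estimate the same quantity and can give different answers. The one sentence that speaks to superiority points to change, while the endpoint and the power section point elsewhere. Leaving this open allows the choice to be made after the data are seen.

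If the Framework sentence were followed literally, there are two further problems.

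- **Precision.** A difference of two yes/no answers takes the values -1, 0 and 1 and carries the noise of both. With randomised arms, a large-sample linear comparison of changes is never more precise than one that adjusts for baseline.
- **Meaning.** The baseline testing item that the SAP describes (Analysis for Aim 1) is whether the participant has ever been tested. The 9-month item covers three months. Subtracting one from the other mixes recall windows and is hard to interpret.

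**Working it through.** **Inputs from the documents.** Control proportion 0.10 and difference 0.15, so 0.25 in the intervention arm. Households 100 and 50 ("level-3 (household) 2:1 intervention: control randomization"), with 2 people per household and 3 timepoints. Within-person correlation below 0.7 and household correlation below 0.3, both used at the bound. Attrition 15%. Alpha 0.05, with "All hypothesis tests will be 2 sided, with a 95% confidence interval".

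**Assumptions, because the documents give no value.** The baseline proportion p0 is the same in both arms: 0.10, 0.25 or 0.50. The baseline-to-9-month correlation r is 0.3 or 0.5. Attrition is taken off the 150 households. Power is Φ(0.15/SE − 1.96) with unpooled variances, a linear large-sample approximation.

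**1. The plan's own figure.** Design effect = 1 + (3−1)(0.7) + 3(2−1)(0.3) = 3.3, applied to 600 and 300 observations.

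- SE = √[3.3(0.1875/600 + 0.09/300)] = 0.0450, power 91.6%.
- After 15% attrition, SE = 0.0488, power 86.8%.
- With a pooled null variance the two powers are 86.4% and 79.8%.

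The stated figure is therefore reproduced, but for a three-timepoint model.

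**2. 9-month comparison, no baseline.** With 170 and 85 people, SE = √[1.3(0.1875/170 + 0.09/85)] = 0.0530, power 80.8%. Without attrition it is 86.6%.

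**3. Change score.** The per-person variance in each arm is V9 + V0 − 2r√(V9·V0), where V = p(1−p). For p0 = 0.10 and r = 0.3:

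- intervention: 0.1875 + 0.09 − 0.6√(0.1875 × 0.09) = 0.1996
- control: 0.09 + 0.09 − 0.6(0.09) = 0.1260
- SE = √[1.3(0.1996/170 + 0.1260/85)] = 0.0588, power 72.3%

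**4. Baseline adjustment.** SE = 0.0530√(1−r²), which is 0.0506 at r = 0.3 (84.3%) and 0.0459 at r = 0.5 (90.4%).

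**5. Household clustering.** Steps 3 and 4 keep a household correlation of 0.3 in the change or residual. Alternatively, the correlation between household members is 0.3 at and across both times (exchangeable), and then much of the shared part cancels. The adjusted variance factor at r = 0.3 becomes (1−0.09) + 0.3(1−0.3)² = 1.057 in place of 1.3.

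Power after 15% attrition:

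| p0 | r | Change, correlation kept | Adjusted, correlation kept | Change, exchangeable | Adjusted, exchangeable |
|---|---|---|---|---|---|
| 0.10 | 0.3 | 72% | 84% | 82% | 88% |
| 0.10 | 0.5 | 85% | 90% | 92% | 94% |
| 0.25 | 0.3 | 56% | 84% | 66% | 88% |
| 0.25 | 0.5 | 69% | 90% | 80% | 94% |
| 0.50 | 0.3 | 48% | 84% | 57% | 88% |

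If the household part cancels completely (factor 1 in place of 1.3), the change score at r = 0.3 has 83% (p0 = 0.10) or 67% (p0 = 0.25).

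Without attrition and with the household correlation kept, the change score has 79% (p0 = 0.10) or 63% (p0 = 0.25) at r = 0.3, and 90% or 76% at r = 0.5. Adjustment then has 90% and 94%.

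**6. Limits on r.** Two yes/no items with proportions 0.10 and 0.25 cannot correlate above √[(0.10 × 0.75)/(0.25 × 0.90)] = 0.58. Values near the plan's 0.7 bound are therefore out of reach in one arm when p0 is 0.10 or 0.25. With p0 = 0.50 the control-arm limit is √[(0.10 × 0.50)/(0.50 × 0.90)] = 0.33, so r = 0.5 is not shown for that row.

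**The case against.** Three stronger readings are tempting, and the documents do not support them.

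**That the SAP has settled on a change-score test.** The Framework sentence is general, refers to the outcomes of interest as a whole, and names no model. The statistical methods write out a logistic model for uptake at each time, and no change-score model appears anywhere. This stands, so the defect is a conflict and not a settled choice. It does not remove the conflict, because neither the cross-sectional nor the longitudinal model is named as primary.

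**That the difference variables prove testing will be differenced.** The examples given are vaccination status, exposure and employment. The list is open-ended, so testing is not excluded, but it is not named either.

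**That power falls below the plan's 80%.** That figure was never calculated for a change score, so it is not a direct comparator. The loss is also conditional: with a baseline proportion of 0.10 and r of 0.5, the change score keeps at least 85% after attrition. Break-even against ignoring baseline comes at r = 0.44 for p0 = 0.10 and r = 0.63 for p0 = 0.25, so no single threshold applies.

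Two further cautions stand. The 1−r² gain is a linear-model result, so 84% and 90% are approximations and not the power of the logistic model proposed below. And the full baseline questionnaire is not in the documents, so an item with a matching recall window may exist.

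**Conclusion.** The concern holds as an unresolved inconsistency. The Framework sentence names a comparison that matches neither the endpoint nor the powered test, and the plan does not say which analysis is primary or adjust it for baseline testing.

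Within each treatment of clustering, adjustment beats the change score in every scenario tabulated. The gap runs from 2 points (p0 = 0.10, r = 0.5, exchangeable) to 36 points (p0 = 0.50, r = 0.3, correlation kept). Change-score power at r = 0.3 lies anywhere from 48% to 83%, depending on the baseline proportion and on how clustering carries over, neither of which the documents settle. No single power loss should be quoted. The mismatch between an ever-tested baseline item and a three-month follow-up item counts against a change score whatever the correlation.

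This should be corrected, but it does not show that the trial is underpowered.

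**What to change.** Replace the Framework sentence with one that names a single primary test. For example: superiority is assessed by the two-sided test of the arm effect on testing uptake at 9 months, in a mixed-effects logistic model with a household random effect and baseline testing as a covariate.

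Then:

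- state under Created Variables that difference variables are not used for the primary efficacy test;
- label the models in Analysis for Aim 4 and Longitudinal Analysis as primary or supportive, and show where the arm term enters;
- state power for the named analysis in Power and Sample Size, giving the assumed r and household correlation;
- say which baseline testing item is the covariate and what recall window it has.

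The cost is SAP wording. No new data are needed if the ever-tested item is used, since a covariate need not share the outcome's recall window. There are two downsides. The odds ratio becomes conditional on baseline testing. And the precision gain will be small if having ever been tested predicts 9-month testing only weakly.

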### **Intervention description {11a}**

#### *Experimental condition*

The NCFP intervention is delivered by nurses and community health workers (CHWs) as part of a collaborative partnership with households over the course of 5 months. On average, there will be three nurse-CHW home visits to households randomized to the intervention condition per month. Each visit will last for approximately 45 minutes on average.

The NCFP intervention prioritizes provision of intervention content based on three household risk levels: low, medium, and high. This intervention will use an algorithm to determine household-level risk to COVID-19. Low risk is defined by experience of no symptoms and no exposures by all household members. Medium risk is defined by experience of either symptoms (i.e. new cough, chest pain, fever above 100.4°, and/or loss of taste or smell) or an exposure to someone with known or suspected COVID-19 by any household member. High risk is established when a household member has a confirmed positive COVID-19 test. The algorithm will be informed by self-report of symptoms and exposures through a nurse hotline that is available for households placed in the intervention arm to use.

Additionally, nurses will conduct weekly phone screenings to continue monitoring household symptoms and exposures. For households that are at low risk, the intervention delivery team will provide the standard intervention content, which consists of (1) development and follow-up of an infection control plan tailored to the unique circumstances of the household, (2) printed NCFP family materials, (3) offer of monthly routine Polymerase Chain Reaction (PCR) COVID-19 test (self-administered saliva test), (4) provision of PPE (masks, hand sanitizer, gloves) and a thermometer, and (5) navigation to at-home or community-based COVID-19 vaccination services, as well as health, social welfare, vocational,

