economic, or other support services as needed. For households that are at medium risk, in addition to the standard intervention content, the intervention delivery team will offer a rapid antigen COVID-19 tests to household members who are experiencing symptoms or were exposed and conduct enhanced symptom monitoring (daily phone screenings of new or worsening symptoms for seven days after report of symptoms or exposure). For households that are at high risk, nurses will additionally offer rapid antigen tests to all household members, enhanced symptom monitoring with all household members, and provide isolation support and guidance. In the event household members display any other acute emergency, nurses and CHWs will coordinate with the clinical triage team, where they will conduct triage, medical case management, monitoring, referrals to care, and follow-up.

In this intervention, nurses will supervise CHWs. Nurses will work with households on clinical and technical COVID-19 related issues, as well as build knowledge and skills that will help mitigate the spread and development of COVID-19 symptoms in households. For instance, nurses will offer routine in-home COVID-19 testing to all members of the household and deliver training on household infection control skills, including the safe and correct use of PPE, frequent use of hand disinfectant and handwashing, and social distancing techniques. The CHWs will serve as a culturally appropriate resource for families randomized to the intervention condition to ensure continued engagement and retention in the Nurse-Community-Family Partnership. CHWs will work with households to address expectancies, norms, and emotions that may represent barriers to COVID-19 testing and other related services. Additionally, CHWs will provide navigation to support services as needed.

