**Statistical methods**

**Statistical methods for primary and secondary outcomes {20a}**

SAS, M Plus, R, and/or Stata statistical software will be used for data analysis; statistical significance will be assessed as  $p < 0.05$ . For the RCT, we will conduct analysis in two stages: cross-sectional analysis at each time point and subsequently conducting longitudinal analysis.

Analyses for primary and secondary outcomes will include a descriptive examination of outcomes for participants at baseline, months 1-6, and 9 months post-baseline. These data are dichotomous (i.e. "Have you ever been diagnosed or tested positive for COVID-19 by a swab or a saliva test?"), nominal (i.e.

COVID-19 symptoms), and continuous (i.e. “If you had to guess, how many of your household/family members have been tested for COVID-19?”) in nature. Bivariate analyses will be conducted to examine associations between testing practices and key predictors (intervention group), confounders (i.e. previous infection or vaccination), moderators (i.e. essential worker status, testing fatigue), and demographic characteristics (e.g., age, gender, race, ethnicity). These differences will be examined in bivariate analyses (unadjusted) and multivariable analysis (adjusted).

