### **Interim analyses {21b}**

The data analysis team will conduct interim analyses every 6 months during the duration of the trial. The data analysis team will review data on recruitment, participant characteristics, protocol compliance, and study outcomes (improve household-level COVID-19 routine testing, household-level COVID-19 indicated testing, COVID-19 vaccine uptake, seasonal influenza vaccine uptake, adoption of COVID-19 control measures, and household-level mutual aid capacity). This analysis will also assess the differential proportion of self-reported COVID-19 infection between the two trial groups (a safety assessment of the trial primary outcome). There are no planned adjustments of the significance level due to interim analysis.

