#### **Composition of the data monitoring committee, its role and reporting structure {21a}**

Data Safety and Monitoring Board will include a statistician/methodologist and two physicians who are highly experienced in study monitoring. The DSMB will review blinded reports of social or clinical outcomes and other adverse events.

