Measurement error. Where possible, we will adopt analytic strategies that explicitly model measurement error, such as using SEM with multiple indicators. For single indicator SEM, measurement error can be modeled by fixing error variances of measures at *a priori* specified values that map onto their reliability as suggested by previous research [8,9]. If it is a multi-item measure, we can create multiple indicators using split-half methods. When we cannot formally model measurement error, we will take care to recognize biasing effects of measurement error when interpreting the results of statistical analyses.

Aim 5 is to use FDA-authorized tests, characterize the community and household epidemiology of SARSCoV2/COVID-19 including prevalence of current infection, incidence of new infection,

symptomatic illness, accessing care, hospitalization and mortality.

Analysis for Aim 5

To address Aim 5, we will estimate current infection using SARS-CoV2 RNA testing of baseline specimens from the intervention group. Incidence of new infection per 100 person-months will be estimated from the results of repeat voluntary in-home RNA and antigen testing (intervention group) and approximated from self-reported results of repeat voluntary tests in the controls. Occurrence of symptomatic illness, accessing COVID-19 care, hospitalization and mortality will be measured in both groups by self-report from family members. Qualitative methods will use a grounded theory approach in which ethnographers identify key themes for further inquiry and analyses and contribute to quantitative data triangulation.

Aim 6 is to (with our community and scientific advisory boards,) develop pilot projects that will address knowledge and implementation gaps that are uncovered as new diagnostic testing is developed and as the investigative team and community partners work together to address Aims 1-5.

Analysis for Aim 6

The analysis plans for Aim 6 will be developed for projects as appropriate.

Power and Sample Size.

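### The interim safety check compares self-reported infection between arms that are tested differently by design, so it mixes infection with detection and can mislead

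*SAP*

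**What the plan says.** **The check.** The SAP (Interim Analyses) has the data team, every 6 months, "assess the differential proportion of self-reported COVID-19 infection between the two treatment groups (a safety assessment of the trial primary outcome". The protocol (Interim analyses {21b}) repeats it: the team will "assess the differential proportion of self-reported COVID-19 infection between the two trial groups". Neither document says which survey item supplies the infection variable, sets the comparison against the amount of testing, or attaches a threshold or action to it.

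**How infection becomes known.** The protocol's example of a dichotomous item (Statistical methods {20a}) is "Have you ever been diagnosed or tested positive for COVID-19 by a swab or a saliva test". The SAP (Confounding Variables) likewise asks about a previous diagnosis.

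**Testing by arm.** In the intervention arm (protocol, Experimental condition), low-risk households get an "offer of monthly routine Polymerase Chain Reaction (PCR) COVID-19 test (self-administered saliva test". Medium-risk households are also offered antigen tests for members with symptoms or exposure. Once a member tests positive, "nurses will additionally offer rapid antigen tests to all household members". Controls are told where free community sites are and receive standard city information (Treatment-as-usual condition). The protocol's rationale gives more screening as the purpose of the intervention, and testing uptake is the primary outcome.

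**Aim 5.** The SAP takes incidence from in-home RNA and antigen tests in the intervention arm, while control incidence is "approximated from self-reported results of repeat voluntary tests in the controls". Symptomatic illness, COVID-19 care, hospitalisation and death are collected in both arms from family members. None of these is tied to the interim check.

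**The concern.** A safety measure should not move merely because the intervention does what it was built to do. This one does. The more the intervention raises testing, the more infections are found in that arm at the same true infection rate, and each case found triggers further test offers to that household. Controls have no such cascade. The distortion runs against the intervention, and it can also cancel a real reduction from protective equipment, vaccination or isolation support.

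This is the only between-arm safety comparison that either document names. The SAP's Harms section records adverse events but plans no comparison of them by arm. The SAP's Final Analysis section allows for the trial being stopped early, and protocol section {22} lets the ethics board halt or modify it. A predictable excess of reported infection could therefore reach decision-makers with nothing to explain it.

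**Working it through.** **Inputs from the documents** (SAP, Power and Sample Size): control proportion 0.10; difference 0.15, hence 0.25 in the intervention arm; 100 v 50 households with 2 individuals each, hence 200 v 100; 3 timepoints; correlations below 0.7 (within individual) and 0.3 (within household); 15% attrition; alpha 0.05, two-sided (SAP, Final Analysis). That section does not name the outcome; the proportions are read here as testing uptake, the primary outcome.

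**The plan's own figure.** Design effect at the limiting correlations: 1 + (3 − 1) × 0.7 + 3 × (2 − 1) × 0.3 = 3.3. Effective sizes: 600 / 3.3 = 181.8 and 300 / 3.3 = 90.9. Power for 0.25 v 0.10 is 86.4% (pooled variance) or 91.6% (unpooled). After 15% attrition it is 79.8% or 86.8%, and higher at lower correlations (85.1% pooled at 0.5 and 0.3). The stated power above 80% is reproduced, so 0.25 v 0.10 is a fair reading of the planned effect. No figure is stated for the infection check.

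**Detection model.** Reported infection = true risk × probability that an infection is detected. Hence

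observed ratio = true ratio × (detection in intervention / detection in control),

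and the arms look equal when the true ratio equals detection in control / detection in intervention. The documents give no detection probabilities; every pair below is an assumption, the first borrowing the planned testing proportions.

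| Detection, intervention v control | Observed ratio, equal infection | Observed ratio, true 20% reduction | Observed ratio, true 40% reduction | True reduction at which arms look equal |
|---|---|---|---|---|
| 0.25 v 0.10 | 2.5 | 2.0 | 1.5 | 60% |
| 0.8 v 0.4 | 2.0 | 1.6 | 1.2 | 50% |
| 0.6 v 0.4 | 1.5 | 1.2 | 0.9 | 33% |
| 0.8 v 0.6 | 1.33 | 1.07 | 0.80 | 25% |
| 0.5 v 0.4 | 1.25 | 1.0 | 0.75 | 20% |
| 0.6 v 0.6 | 1.0 | 0.8 | 0.6 | 0% |

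For example, with 10% truly infected in both arms and detection 0.25 v 0.10: 0.10 × 0.25 = 2.5% (5 of 200) against 0.10 × 0.10 = 1.0% (1 of 100).

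**How often it would show.** 20,000 simulated trials per setting, 200 v 100 individuals, equal true infection, pooled z test, household clustering ignored. Each cell gives the percentage of trials in which the intervention arm shows the higher proportion, then the percentage in which the excess is nominally significant (z > 1.96).

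| True infection risk (assumed) | 0.25 v 0.10 | 0.8 v 0.4 | 0.6 v 0.4 |
|---|---|---|---|
| 10% | 81 / 5 | 91 / 23 | 76 / 8 |
| 20% | 91 / 20 | 98 / 50 | 85 / 16 |
| 30% | 95 / 31 | 99.5 / 72 | 91 / 26 |
| 40% | 97 / 43 | 99.9 / 86 | 95 / 36 |

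An apparent excess is the usual result under these gaps; a significant one is not assured. The SAP's Design section gives 400 individuals rather than 300. That would change the percentages, but not the ratios.

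**The case against.** Much can be said for the plan, and most of it limits the point rather than removing it.

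- **Infection is not reported only through tests.** The example item also accepts a diagnosis, and the surveys ask about current illness and symptoms. This stands: the dependence on testing is large, not total.
- **A reader might infer that a working intervention will look harmful, by a factor of 2.5.** The documents do not support this. The 0.25 and 0.10 are uptake proportions, not detection given infection, and testing is partly prompted by symptoms or exposure. If infected controls seek tests, the gap narrows: at 0.6 v 0.4 a true halving shows as 0.5 × 1.5 = 0.75, a visible benefit. The real detection ratio is unknown.
- **Testing data are reviewed at the same interim.** Protocol section {21b} lists routine and indicated testing among the outcomes reviewed. That helps, but nothing says they are shown by arm beside infection or used to interpret it.
- **A reader might infer a false stop.** No threshold or action depends on the check, and the protocol plans no discontinuation of the intervention ({11b}).
- **A reader might infer that Aim 5 has a flawed between-arm test.** It plans none. Its stated purpose is descriptive, and the SAP concedes that the control figure is approximate. The difference in ascertainment matters only if the arms are compared or pooled. Using self-report in both arms would not cure it, since intervention participants would still be reporting results of the extra tests.
- **A reader might infer that the by-arm table should go to the monitoring board.** The protocol keeps the board blinded ({17a}) and states that "The DSMB will review blinded reports of social or clinical outcomes and other adverse events". Changing that is a separate governance question.

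**Conclusion.** The point holds in this form: the interim safety check compares an outcome seen mainly through testing or diagnosis, in a trial that raises testing in one arm by design, and nothing in either document allows for it. Any detection gap in the intended direction biases the comparison against the intervention. The size is unknown. Over the unequal detection pairs examined, equal infection appears as a ratio of 1.25 to 2.5, and a true reduction of 20% to 60% would be cancelled. The upper end assumes that detection follows the planned testing proportions; if detection were equal, there would be no bias. The model also assumes that reported infection is simply true infection multiplied by detection. The consequence is a safety reading that can mislead in either of two ways: apparent harm, or a concealed benefit.

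**What to change.** In SAP Interim Analyses and protocol section {21b}:

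- Do not use the raw difference in reported infection alone as the safety measure. Show it by arm beside the number tested, tests per person and positivity. Take these from the same survey items in both arms, because study-documented tests exist in one arm only.
- State in advance that more detected infection is expected with more testing, and that positivity is not a full correction: routine testing of people without symptoms lowers it.
- Add hospitalisation and death by arm, already collected in both arms under Aim 5, as the measures least dependent on testing.
- Symptomatic illness and care access may be shown, with the caveat that the intervention's symptom monitoring and service navigation can raise their reporting.

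In SAP Analysis for Aim 5, report incidence separately by arm, and state that ascertainment differs and that the arms are not to be compared or pooled.

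**Cost.** SAP wording, table shells and a change to protocol section {21b}, which under section {25} needs ethics approval before use. The outcome data are already planned. The downside is precision: hospitalisations and deaths will be few in about 300 people, so their absence of difference should not be read as proof of safety.
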